## Statistical analysis

We will use logistic regression to estimate the propensity score of receiving a specific booster dose given covariates as predictors. We will match (without replacements) on age, calendar time of last mutual vaccine dose (i.e., third or fourth dose), and the propensity score (with a calliper width of 0.01).

Cumulative incidences will be estimated by the Kaplan-Meier estimator, and from these we will calculate the comparative VE as 1 – risk ratio at day 365. The corresponding 95% CI will be calculated using the delta method. Country-specific estimates will be combined by random-effects meta-analyses implemented using the *mixmeta* package in R.

Comparative waning will be estimated using meta-regression.(39) First, we will estimate the VEs (in the specific comparison being evaluated) in each consecutive three-months period (day 8-90, day 91-180, 181-270, and 271-365) by stratification on time since booster vaccination. Second, the resulting estimates will be analysed using meta-regression to provide a ratio of VEs per three-month intervals as a measure of waning.

Subgroup analyses will be conducted according to sex, age groups ( $</\ge70$  years), time since last SARS-CoV-2 infection (<6, 6-12, >12 months), time between primary course and first booster ( $</\ge12$  months), time between first and second booster ( $</\ge12$  months), and bivalent booster brand (Pfizer-BioNTech and Moderna).

*All-cause mortality (objective #3)* 

We will examine risk of all-cause mortality at 3, 6, and 9 months since recovery from first Covid-19 hospitalisation. The source population for this cohort will be the same as the main cohort for the main comparative analyses (i.e., individuals aged ≥50 years who have received at least 3 doses of vaccine and no previous Covid-19 hospitalisation prior to study start). Recovery will be defined as discharge from an inpatient hospital stay for Covid-19 (i.e., similar to the outcome definition used in the main analyses). We will start follow-up on day 8\* since discharge, to ensure that there are no rapid rehospitalisations (if this occurs, the individual, can re-enter the cohort on day 8\* after discharge from the re-hospitalisation) and end follow-up on outcome event of all-cause mortality; emigration; Covid-19 vaccination; day 90, 180, or 270; or end of study period. Since this is likely to be a cohort of limited size, we will utilize a complete cohort analysis using multivariate Cox regression model with covariate adjustment (same covariates as main analyses, except not previous SARS-CoV-2 infection, and including length of hospitalization). The exposure (Covid-19 vaccination status [4 vs 3 doses]) will be evaluated at time of Covid-19 hospitalisation (admission date). Dependent on data availability we will consider further categorization of the associations according to subgroups similar to those of the main cohort analyses.

\*Day 8 is a prespecified arbitrary best guess. The final grace period will be determined by examining the distribution of days after discharge for any rehospitalisations in the Danish data. Depending on the data distribution, we will decide if it is necessary to perform additional sensitivity analysis in this regard.

*Immunocompromised (objective #4)* 

In secondary cohorts of individuals aged  $\geq 18$  years with presumed immunocompromised conditions, we will evaluate the effectiveness of the bivalent boosters received as the  $\geq 4$ th dose. We will utilize the same analytical matched approach as in the main analysis described above. Dependent on the data distribution, time of VE assessment may be day 180 or day 365 since booster vaccination. Similarly, dependent on data availability, we will further subgroup bivalent booster recipients according to booster received as fourth, fifth, or  $\geq$ sixth dose, and we will endeavour to assess similar subgroups as in the main cohort subgroup analyses including waning VE analysis. The VE estimates will be indirectly compared with the VE estimates from the main cohort analysis while stressing the limitations of such indirect comparisons.

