In contrast to infection, the bivalent boosters appear to protect well against severe Covid-19 outcomes such as hospitalisation and death.(5–11) In an early US study, a bivalent booster dose offered significant additional protection against Covid-19-associated hospitalisations among adults aged 65 and older.(6) When compared to unvaccinated individuals, the vaccine effectiveness was 84%, and when compared to individuals who had received two or more doses of monovalent mRNA vaccines it was 73%. In Israel, the comparative effectiveness of a bivalent booster dose in reducing

hospitalisations and deaths due to Covid-19 in individuals aged 65 years or older was evaluated in a study cohort comprising 569,519 participants, including 134,215 (24%) who were given a bivalent booster.(9) The results showed that those who received the bivalent mRNA booster had a lower rate of Covid-19 related hospitalisations compared to those who did not receive the booster corresponding to an effectiveness of 72%. These findings emphasise the importance of bivalent mRNA booster vaccinations in populations at high risk of severe Covid-19. In a larger cohort of individuals aged 12 years or older from North Carolina, a bivalent booster (1.07 million vaccine recipients) was more effective than a monovalent booster (292,659 individuals), with a vaccine effectiveness of 61.8% against severe infection resulting in hospitalisation or death, compared to 24.9% for the monovalent booster. (7,8) Evidence of waning was observed after a peak at 4 weeks, although less pronounced for the bivalent booster. The Moderna and Pfizer-BioNTech bivalent boosters showed similar effectiveness. In our recent Nordic study, we examined the comparative vaccine effectiveness of the bivalent mRNA-booster vaccines in 3.37 million individuals aged 50 or older.(1) The study found that receipt of a bivalent BA.4-5 booster as a fourth dose was associated with a country-combined VE against Covid-19 hospitalisation of 67.8%, while the corresponding VE for bivalent BA.1 boosters was 65.8%. In addition, we observed no significant difference between BA.4-5 and BA.1 boosters when directly compared.

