## **Primary objectives:**

1. To provide estimates of VE against severe Covid-19 outcomes at day 365 after immunisation with a BA.1 or BA.4-5 bivalent booster as a fourth dose, comparing a) the BA.1 and BA.4-5 bivalent booster against not having received a fourth dose and b) between the BA.1 and BA.4-5 bivalent and the original monovalent booster.

- 2. To provide estimates of waning of VE against severe Covid-19 outcomes as the three-monthly relative reduction in vaccine effectiveness until day 365 after immunisation with a BA.1 or BA.4-5 bivalent booster as a fourth dose, comparing a) the BA.1 and BA.4-5 bivalent booster against not having received a fourth dose and b) between the BA.1 and BA.4-5 bivalent and the original monovalent booster.
- 3. To provide estimates of VE against all-cause mortality at 3, 6, and 9 months post discharge for COVID-19 hospitalisation, comparing a) individuals who received BA.1 and BA.4-5 bivalent boosters as fourth dose against individuals not having received a fourth dose and b) individuals who received the BA.1, BA.4-5 bivalent, or original monovalent boosters.

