of interest		protocol effect.
Statistical analysis	Kaplan-Meier estimator to obtain cumulative incidence for each treatment strategy during follow-up. Compare cumulative incidence across treatment strategies by risk ratios (to obtain VE) and risk differences.  Person-time since baseline will be stratified consecutive in three-months periods with the Kaplan-Meier estimator to estimate third-monthly changes in VEs; these VEs will contribute to meta-regression estimating comparative waning.	Same as for the target trial except observational analogs of perprotocol.

Subgroup analyses by sex (female/male), age ( ≥70 years), time between vaccine dose (between primary</th 	course and 3rd dose and 3rd and 4th dose; for	
general population target trial), and vaccine brand	
(Pfizer-BioNTech/Moderna).	

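### Waning is defined as a ratio of vaccine effectiveness (VE) values, which is unstable or meaningless when VE is near or below zero, as is likely for BA.4-5 versus BA.1

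*Protocol*

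**What the plan says.** Section 9.7 (Statistical analysis) defines effectiveness from cumulative incidences: "we will calculate the comparative VE as 1 – risk ratio at day 365". For waning, VE is estimated in four consecutive periods ("day 8-90, day 91-180, 181-270, and 271-365) by stratification on time since booster vaccination"), and the results are then "analysed using meta-regression to provide a ratio of VEs per three-month intervals as a measure of waning".

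The same scale appears elsewhere. Primary objective 2, in the abstract and in section 8, asks for waning "as the three-monthly relative reduction in vaccine effectiveness until day 365 after immunisation". The target trial table in section 9.1 uses the periods "to estimate third-monthly changes in VEs; these VEs will contribute to meta-regression estimating comparative waning". Objective 2 covers the four versus three dose comparisons and also those "between the BA.1 and BA.4-5 bivalent and the original monovalent booster".

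Section 7 gives the only Nordic effectiveness figures, from the authors' previous study: 67.8% for BA.4-5 and 65.8% for BA.1 against Covid-19 hospitalisation, each as a fourth dose. It adds that "we observed no significant difference between BA.4-5 and BA.1 boosters when directly compared". The protocol neither names the log risk ratio as the modelled scale nor says what happens when a period VE is zero or negative.

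**The concern.** A ratio of two effects can be read only if the denominator is clearly away from zero and both values have the same, favourable sign. VE does not guarantee this: it is zero at RR 1 and negative above it. Near zero, small random differences between periods produce very large ratios of either sign. Below zero the direction misleads, because a fall in VE from −5% to −20% gives a ratio of +4.0.

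Between two boosters of similar effectiveness, VE near zero is a likely state of affairs from the start. The measure belongs to a primary objective, so the waning result for BA.4-5 versus BA.1 could be mostly noise, or could suggest waning where there is none.

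**Working it through.** The protocol states no waning figure to reproduce, so the check is how the stated measure behaves at the protocol's own effect sizes.

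**Inputs.** VE 67.8% (BA.4-5) and 65.8% (BA.1), from section 7; VE = 1 − RR and four periods, from section 9.7. The precision per period is an assumption: standard error (SE) of log RR of 0.10 or 0.05. If log RR has variance 1/e + 1/e, with e events in each arm, these correspond to about 200 and 800 events per arm (√(2/200) = 0.10; √(2/800) = 0.05). The protocol does not split its expected events by booster, matched set and period.

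**Step 1: implied BA.4-5 versus BA.1 effect.** RR = (1 − 0.678)/(1 − 0.658) = 0.322/0.342 = 0.942, so VE is about 5.8%. This is an indirect figure.

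**Step 2: chance of a negative VE in one period, with no waning.** P(VE < 0) = P(Z > −ln(RR)/SE), with −ln(0.9415) = 0.0603.
- SE 0.10: P(Z > 0.603) = 27%. At least one of four independent periods: 1 − (1 − 0.273)^4 = 72%.
- SE 0.05: P(Z > 1.205) = 11% (12% if RR is first rounded to 0.942). At least one of four: 38 to 39%.

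**Step 3: ratio of two period VEs when the true ratio is 1.** Simulation of two independent periods at RR 0.942:

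| SE of log RR | VE ratio: median (95% range) | Negative | Ratio of RRs: median (95% range) |
|---|---|---|---|
| 0.10 | 0.32 (about −11 to +12) | 40% | 1.00 (0.76 to 1.32) |
| 0.05 | 0.75 (about −8.5 to +10.7) | 20% | 1.00 (0.87 to 1.15) |

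The negative share agrees with 2p(1 − p): 2 × 0.273 × 0.727 = 40% and 2 × 0.114 × 0.886 = 20%. The ratio-of-RRs range agrees with exp(±1.96 × √2 × SE). The VE ratio is centred below 1 although nothing wanes.

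**Step 4: do more events cure it?** Not if the boosters are equal. At RR 1.0 each period VE is at or below zero with probability one half, so at least one of two is so in 1 − 0.5² = 75% of cases, whatever the event count. At RR 0.90 more events do help: with 100, 300, 500 and 1,000 reference-arm events per period the figure is 41%, 20%, 10% and 2%.

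**Step 5: four versus three doses.** Start at RR 0.322 and multiply RR by a constant factor per period.

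| Factor | VE in periods 1 to 4 | Successive VE ratios |
|---|---|---|
| 1.10 | 67.8, 64.6, 61.0, 57.1% | 0.95, 0.95, 0.94 |
| 1.25 | 67.8, 59.7, 49.7, 37.1% | 0.88, 0.83, 0.75 |
| 1.40 | 67.8, 54.9, 36.9, 11.6% | 0.81, 0.67, 0.32 |
| 1.50 | 67.8, 51.7, 27.5, −8.7% | 0.76, 0.53, −0.32 |

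With slow waning the ratio is stable and usable. VE near zero by period 4 needs RR to rise about 1.4- to 1.5-fold per period. With faster waning, a constant change in RR does not give a constant VE ratio, so one ratio per three months would describe it poorly.

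**The case against.** **The wording may be loose.** The method is cited to a published waning study that is not at hand, and the modelling scale is often left to a statistical analysis plan. A ratio of risk ratios may be what is meant. That is possible, but the objective, the target trial table and the analysis section all state the VE scale, and the objective itself names a relative reduction in VE. If a ratio of risk ratios is intended, those places misstate it and need the same correction. The table's mention of changes in VE could also be read as differences, which exist for any sign; the other places specify a ratio or a relative reduction.

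**The numbers are illustrative.** This stands. RR 0.942 divides estimates from two separately matched comparisons, and section 9.9 says such results should mainly be read separately. A non-significant difference is not proof of a VE near zero. The standard errors are assumed, and a two-period ratio is not the slope of a four-period, four-country meta-regression. The ranges show how the measure behaves, not the interval the study would report.

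**Readings the protocol does not support.** A reader might infer that VE near zero is expected late in the four versus three dose comparisons. No late VE is given: section 7 notes that existing follow-up does not go beyond 2 to 6 months and that waning was less pronounced for the bivalent booster. A reader might also infer that periods with VE at or below zero would be dropped, with bias towards less waning, or that log VE is modelled; the protocol states neither. Nor does the argument extend to every between-booster contrast. For bivalent versus monovalent there is no Nordic figure, and section 7 cites 61.8% against 24.9% from another cohort.

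**Conclusion.** The concern holds: the waning measure for primary objective 2 is wrong as written. It is unstable or uninterpretable when VE is near or below zero, which is likely for BA.4-5 versus BA.1 on the protocol's own evidence. At an indirect RR of about 0.94 and an assumed SE of log RR of 0.05 to 0.10, a negative VE in any one period has a chance of roughly 11 to 27%, and a two-period ratio can take almost any value of either sign. For four versus three doses the weakness is conditional: it would appear only if protection wanes fast enough to approach zero by the last period, which is possible but not documented.

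**What to change.** In section 9.7, meta-regress the period-specific log RR on period number, combining countries with random effects, and report exp(slope), the ratio of risk ratios per three months, as the waning measure. A value above 1 means that relative protection is declining. It is defined for any VE, and reversing the reference booster only inverts it. Show the period-specific VEs with intervals beside it; section 12 already plans figures of waning VE. Reword primary objective 2 in the abstract and section 8, and the statistical analysis row of the target trial table in section 9.1, to match.

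This needs no new data, only a change of modelled quantity and edits in four places. The price is that the headline waning figure is no longer expressed directly as a relative change in VE, so readers will need the period VEs to translate it.

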### Secondary objectives:

4. To provide VE estimates at day 90/180/365 (pending data distribution) after immunisation with a bivalent booster among immunocompromised individuals.

- 5. To provide VE estimates at day 365 after immunisation with a bivalent booster among females and males, and 50-69-year-olds and 70+-year-olds.
- 6. To provide VE estimates at day 365 after immunisation with a bivalent booster according to time since a previous infection.
- 7. To provide VE estimates at day 365 after immunisation with a bivalent booster according to time between-dose intervals (for both the primary course and the booster doses).
- 8. To provide VE estimates at day 365 after immunisation with a bivalent booster according to the vaccine brand received as fourth dose.

**Study design**: Nationwide register-based cohort analyses in Denmark, Finland, Norway, and Sweden during the study period from 27 December 2020 until latest available date in 2023 at time of analyses (e.g., 30 September 2023).

Population: Source cohorts will consist of all individuals who are known residents in the four Nordic countries and have received at least three vaccine doses (i.e., a primary two-dose vaccination course and one booster) with the AZD1222 (Vaxzevria, Oxford-AstraZeneca; as part of the primary vaccination only), BNT162b2, and/or mRNA-1273 vaccines between 27 December 2020 and latest available date in 2023. The main study cohort will consist of individuals who are at least 50 years of age in Denmark, 60 in Finland, 65 in Norway, and 50 in Sweden and eligible fourth dose recipients will include those receiving a fourth dose after (including on this day) 1 September 2022 in Denmark, 18 July 2022 in Finland, and 1 July 2022 in Norway and Sweden. Secondary study cohorts will consist of 1) main study cohort individuals hospitalized for Covid-19 and 2) immunocompromised individuals aged ≥18 years.

**Variables**: The outcomes of interest will be Covid-19 hospitalisation, Covid-19 mortality and all-cause mortality for the third primary objective. Covariates will be variables of demography, comorbidity, and previous Covid-19 infection and vaccination.

**Data sources**: Nationwide demography- and healthcare registers within each participating country.

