## 8. RESEARCH QUESTION AND OBJECTIVES

The aim of this project is to evaluate the comparative effectiveness of the bivalent boosters in preventing severe Covid-19 outcomes and all-cause mortality among individuals aged 50 years or older with 1-year of follow-up.

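### Objective #3, the only all-cause mortality analysis, is labelled VE but follows only patients discharged alive, so in-hospital deaths are not counted and any booster benefit on them is missed

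*Protocol*

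**What the plan says.** The aim in Protocol section 8 is effectiveness in "preventing severe Covid-19 outcomes and all-cause mortality among individuals aged 50 years or older with 1-year of follow-up". Primary objective 3 is worded "To provide estimates of VE against all-cause mortality at 3, 6, and 9 months post discharge for COVID-19 hospitalisation". The abstract (section 4, Variables) ties all-cause mortality to this objective alone: "The outcomes of interest will be Covid-19 hospitalisation, Covid-19 mortality and all-cause mortality for the third primary objective". The example results table in section 12 agrees, since its only outcome columns are Covid-19 hospitalisation and Covid-19 death.

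The analysis is set out in section 9.7 under all-cause mortality:

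- **Exposure.** Vaccination status, four against three doses, "will be evaluated at time of Covid-19 hospitalisation (admission date").
- **Entry.** "Recovery will be defined as discharge from an inpatient hospital stay for Covid-19". Follow-up starts on day 8 after discharge, and a footnote says "Day 8 is a prespecified arbitrary best guess".
- **Exit.** The plan is to "end follow-up on outcome event of all-cause mortality; emigration; Covid-19 vaccination; day 90, 180, or 270; or end of study period".
- **Model.** Cox regression in the whole cohort, adjusted for the main covariates except previous infection, plus length of the hospital stay.

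The limitations in section 9.9 do not mention selection on survival to discharge. Collider bias appears there only as the reason for not studying hybrid immunity.

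**The concern.** Exposure is fixed on one date, and entry depends on being alive at a later one. The condition for entry is survival, which is the outcome, and it is applied after exposure has been classified. A patient who dies during the index stay is never at risk in this analysis, even in registers that record a discharge as deceased, because follow-up begins on day 8 after discharge.

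This has two consequences if boosted patients are less likely to die in hospital.

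1. The benefit is not counted, whatever the frailty of the patients concerned.
2. Patients whose in-hospital death was prevented enter the four-dose group, while their three-dose counterparts have been removed. If those saved are frailer than other survivors in ways the covariates miss, four-dose mortality after discharge rises relative to three-dose mortality.

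The grace-period check planned in the section 9.7 footnote does not address this. Moving day 8 to any other day, including the day of discharge, recovers no in-hospital death. At stake is the meaning of the study's only all-cause mortality result, which carries the name of a vaccine effect.

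**Working it through.** **Figures in the plan.** There is none to reproduce on this point. The protocol gives no in-hospital mortality, no mortality after discharge and no event count for objective #3. Its only size figure, at least 2,250 hospitalised four-dose recipients (section 9.5), comes without underlying rates.

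**Assumed inputs.**

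- h, in-hospital death with three doses: 5% or 10%.
- h4, the same with four doses: h × (1 - reduction), with a reduction of 0 or 50%.
- m, nine-month mortality after discharge in other survivors: 15%.
- s, nine-month mortality in those whose in-hospital death was prevented: 15%, 30% or 50%.
- No other booster effect.

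**Formulas.**

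- After discharge: three doses = m; four doses = [(1 - h)m + (h - h4)s] / (1 - h4).
- From admission: three doses = h + (1 - h)m; four doses = h4 + (1 - h)m + (h - h4)s.
- VE = 1 - four-dose risk / three-dose risk.

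**Worked case: h = 10%, reduction 50%, s = 30%.**

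- After discharge: (0.135 + 0.015)/0.95 = 15.8% against 15.0%. RR 1.053, VE -5.3%.
- From admission: 0.05 + 0.135 + 0.015 = 20.0% against 0.10 + 0.135 = 23.5%. RR 0.851, VE +14.9%.
- Share of three-dose deaths never counted: 0.10/0.235 = 43%.

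**Other cases by the same formulas.**

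| h | Reduction | s | VE after discharge | VE from admission |
|---|---|---|---|---|
| 10% | 50% | 15% | (0.135 + 0.0075)/0.95 = 15.0%: 0% | 0.1925/0.235: +18.1% |
| 10% | 50% | 50% | (0.135 + 0.025)/0.95 = 16.8%: -12.3% | 0.210/0.235: +10.6% |
| 5% | 50% | 30% | (0.1425 + 0.0075)/0.975 = 15.4%: -2.6% | 0.175/0.1925: +9.1% |
| 5% | 50% | 50% | (0.1425 + 0.0125)/0.975 = 15.9%: -6.0% | 0.180/0.1925: +6.5% |
| any | 0 | any | 0% | 0% |

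The first row separates the two mechanisms. With no extra frailty in those saved, the post-discharge estimate is exactly null while a benefit from admission of 18% goes unrecorded. The last row shows that the distortion needs a booster effect on in-hospital death.

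**Second check, different model.** I simulated 400,000 admissions with log-normal frailty (SD 1), no booster effect after discharge, and an unadjusted Cox model from day 8 among survivors.

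| In-hospital death, three doses | Risk ratio for in-hospital death | Horizon | Cox HR after discharge (SE) | RR from admission |
|---|---|---|---|---|
| 10% | 0.5 | 90 days | 1.07 (0.02) | 0.77 |
| 10% | 0.5 | 270 days | 1.04 (0.01) | 0.89 |
| 5% | 0.7 | 90 days | 1.00 (0.02) | 0.90 |

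The direction is the same, and the shift after discharge is small.

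**Simplifications.** The closed-form arithmetic uses risk ratios rather than hazard ratios, ignores the first days after discharge, and measures the nine months after the stay in both versions. Neither check includes covariate adjustment.

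**The case against.** **The restriction is the declared question.** Objective 3 says post discharge, and mortality after recovery is a legitimate thing to study. This stands, and the post-discharge model should stay. What it does not justify is the VE label on a contrast among survivors, as the only answer to the all-cause mortality part of the aim.

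**The deaths are counted elsewhere.** A reader might infer that in-hospital deaths are lost to the study. The protocol does not support that. Under objectives 1-2, Covid-19 death is death within 30 days of a positive PCR test in Denmark, Finland and Sweden, and a Covid-19 cause of death in Norway (section 9.3). Many index in-hospital deaths qualify. It is, however, a different outcome in a matched cohort indexed at vaccination, so it cannot be added to objective #3 to give mortality after admission.

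**The results are already to be called associations.** Section 12 uses that word for the all-cause mortality tables, and section 9.7 uses it too. This narrows the gap to the VE wording in sections 4 and 8 and the silence in section 9.9.

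**The size rests on an undocumented input.** This is the strongest reply. Section 7 reports VE against hospitalisation (67.8% and 65.8% in the earlier Nordic study). It gives no fatality among those admitted. Strong population protection against death is compatible with preventing admissions and leaving fatality after admission unchanged, in which case there is no distortion. Adjustment for age, comorbidity, priority group and length of stay may also absorb part of the frailty difference. It cannot restore the uncounted deaths.

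**Conclusion.** The point holds as one of labelling and of a missing companion analysis. Objective #3 excludes every death during the index stay by a condition applied after exposure is classified, calls the result VE against all-cause mortality, and gives no caveat.

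With 10% in-hospital death, a 50% reduction and 15% nine-month mortality, post-discharge VE is about -5% to -12%, against about +11% to +15% from admission. At 5% in-hospital death the post-discharge shift is about -3% to -6%. All these inputs are assumptions.

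A reader might infer that an effective booster will appear harmful, or that the primary mortality objective will be answered with the wrong sign. The documents do not establish that. It requires both an effect on fatality after admission and frailty that the covariates miss. The likelier result is an estimate near null that omits the in-hospital benefit, if there is one.

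A reader might also take an analysis from admission as the missing VE against all-cause mortality. It is not: it still conditions on hospitalisation, which follows vaccination and which the booster affects.

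**What to change.** - **Section 9.7, objective #3:** keep the post-discharge Cox model. Add a companion analysis with time zero at the admission date, where exposure is already classified, counting all deaths at 3, 6 and 9 months. Leave length of stay out of that model, because it is determined after admission and is cut short by in-hospital death.
- **Reporting (section 12):** tabulate in-hospital deaths by dose group beside the post-discharge result.
- **Sections 4 and 8, objective 3:** replace VE with an association conditional on surviving the Covid-19 stay, in line with the wording already used in section 12.
- **Section 9.9:** state that the post-discharge analysis selects on survival to discharge, and that both analyses condition on hospitalisation, so neither gives VE against all-cause mortality in the general population aged 50 or older.

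The cost is protocol wording, one extra model and one extra table. Admission and discharge dates are already needed for length of stay in all four countries, and vital status is held. The mortality message becomes less simple.

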#### 9. RESEARCH METHODS

## 9.1 Study design

We will take advantage of the unique nationwide register-data available to us, and construct country cohorts with individual-level information on dates of vaccination and dates of effectiveness end-points together with relevant covariate information. All Nordic residents are assigned a unique personal identifier at time of birth or immigration, enabling linkage between registers. The four Nordic

countries have universal and tax-financed healthcare systems and reporting to national registers is mandatory, providing near-complete follow-up of all residents over time. The cohort participants will be classified according to Covid-19 vaccinations received and followed up using survival analysis. We will utilize comparative designs avoiding comparisons with unvaccinated individuals. This will reduce concern about selection bias due to inherent differences in who chooses to remain unvaccinated.

The study period will start on 1 September 2022 in Denmark, 18 July 2022 in Finland, and 1 July 2022 in Norway and Sweden. These country-specific start dates correspond to when fourth dose vaccination was offered to the general public within the respective country. The study period will end on last date of data availability at time of analyses during autumn 2023 (tentative date: 30 September 2023).

The overall research design builds on target trial emulation methodologies to infer causal relative and absolute effect estimates according to average treatment effect among treated. Key components of the specification and emulation of the pragmatic target trials of the effectiveness of the bivalent Covid-19 booster vaccines against severe Covid-19 using Nordic nationwide registry data are including in table below.

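### Primary objective 3 asks for VE at 3, 6 and 9 months, but the Cox model named for it gives hazard ratios, not the risk-ratio VE that the protocol defines

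*Protocol*

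**What the plan says.** - **Objective.** Section 8 (and the Abstract) lists as primary objective 3: "To provide estimates of VE against all-cause mortality at 3, 6, and 9 months post discharge for COVID-19 hospitalisation".
- **Definition of VE.** The target-trial table in section 9.1 says "Compare cumulative incidence across treatment strategies by risk ratios (to obtain VE) and risk differences". Section 9.7, Statistical analysis, takes Kaplan-Meier cumulative incidences, "and from these we will calculate the comparative VE as 1 – risk ratio at day 365". No other definition of VE appears.
- **Type of effect promised.** Section 9.1 says the overall design is meant to "infer causal relative and absolute effect estimates according to average treatment effect among treated".
- **Analysis of objective 3.** The all-cause mortality part of section 9.7 opens with "We will examine risk of all-cause mortality at 3, 6, and 9 months since recovery from first Covid-19 hospitalisation". Because the cohort is expected to be small, "we will utilize a complete cohort analysis using multivariate Cox regression model with covariate adjustment". Besides death, follow-up ends at "emigration; Covid-19 vaccination; day 90, 180, or 270; or end of study period".
- **Output.** Section 12 lists tables of association estimates for the mortality cohort, and tables of effectiveness estimates for the main and immunocompromised cohorts.

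**The concern.** The objective names a quantity at three time points, and the method named for it produces a different one. A covariate-adjusted Cox model yields a conditional hazard ratio averaged over follow-up from the start of observation. It equals neither the risk ratio at the end of the window nor a risk difference. If the effect changes over time, the average also depends on how many patients are still under observation late in the window, so two countries with the same true risks but different censoring would report different values.

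At stake is one of the three primary objectives. If 1 - HR were tabulated as VE at 9 months, it would sit beside VEs for objectives 1 and 2 that are on the risk-ratio scale. It would tend to be too high if protection fades, and the absolute effect promised in section 9.1 would be absent.

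**Working it through.** **Inputs from the protocol.** The horizons are days 90, 180 and 270. Censoring is by later Covid-19 vaccination, emigration and study end. The tentative study end is 30 September 2023 (section 9.1). The protocol gives no post-discharge mortality, hazard ratio or censoring rate for objective 3, so it contains no figure to reproduce.

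**Assumed inputs.** Two equal groups, no covariates, flat comparator hazard, independent censoring, time counted from discharge, and one Cox fit per horizon.

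**1. Constant hazard ratio.** With comparator risk p0, RR = (1 - (1 - p0)^HR) / p0. For HR = 0.70, 1 - HR is 30.0% whatever the risk.

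| p0 at day 270 | 1 - RR | Excess of 1 - HR |
|---|---|---|
| 10% | 28.9% | 1.1 points |
| 20% | 27.7% | 2.3 points |
| 30% | 26.4% | 3.6 points |

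This is the pure difference of scale. It needs neither fading nor censoring.

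**2. Fading effect.** HR 0.6 to day 90, then 1.0; comparator mortality 20% at day 270.

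- Comparator survival at day 270 is 0.80.
- Boosted survival is 0.80^((0.6 + 1.0 + 1.0)/3) = 0.80^0.867 = 0.824, so boosted risk is 17.6%.
- RR = 17.6/20.0 = 0.879, so 1 - RR = 12.1%. The risk difference is 2.4 points.

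For the Cox model I took the large-sample limit, which is the root of the partial-likelihood score equation, for a fit ended at each horizon.

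| Fit to day | 1 - RR | 1 - HR, no censoring | 1 - HR, exponential censoring of mean 300 days |
|---|---|---|---|
| 90 | 39.1% | 40.0% | 40.0% |
| 180 | 18.8% | 20.7% | 23.6% |
| 270 | 12.1% | 14.3% | 18.4% |

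At day 270 the excess is 14.3 - 12.1 = 2.2 points without censoring and 18.4 - 12.1 = 6.3 points with it. The true 1 - RR is the same in both columns; only the censoring differs. Censoring of mean 300 days leaves exp(-270/300) = 41% uncensored at day 270.

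**3. Is censoring to be expected?** Yes, by design. Counting 270 days back from 30 September 2023 gives 3 January 2023, so nobody discharged after that date can reach day 270. Later vaccination adds to this.

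**The case against.** The other side has several good points.

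- **The protocol does not say that it will fit one hazard ratio, or that VE will be 1 - HR.** This is right. Follow-up ending at day 90, 180 or 270 reads most naturally as one fit per horizon, and the calculation above assumes that. A reader might infer that a single averaged hazard ratio would make fading protection look durable. The text does not support this: with separate fits the fade is plain (40.0%, 20.7%, 14.3% without censoring).
- **The 1 - risk ratio formula is written for day 365 in the matched analysis, and the target-trial table does not list objective 3.** This is also right. The link rests on the shared term VE, which has no other definition, and on the general promise in section 9.1. A reader might also infer a conflict with the statement in section 9.9 that the estimands are effects among the treated. That statement is tied to matching, which objective 3 does not use.
- **Extracting risks from a Cox model can be left to an SAP.** This stands in part. However, the protocol itself chooses the model, states the target as a risk at three times, and calls the output association estimates in section 12. Objective, method and output should agree in the protocol.
- **The size depends on assumptions.** It does. Heavier censoring gives larger gaps: a mean of 120 days gives 24.4% against 12.1%, but leaves only about 10% uncensored at day 270. Nothing in the protocol supports such a rate, so I do not rely on it.
- **The cohort is small.** Section 9.5 expects at least 2,250 hospitalised four-dose recipients, so a model with period-specific effects may be thin in late follow-up. This limits how flexible the model can be; it does not prevent reporting risks.

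**Conclusion.** The concern holds in a limited form. Objective 3 asks for VE at three fixed times, VE is defined only on the cumulative-incidence scale, and the named analysis does not deliver that quantity or any absolute effect. If 1 - HR were used in its place, the 9-month figure would be too high under a fading effect. In the example the excess is about 2 points without censoring and about 6 points with censoring of mean 300 days. With a constant HR of 0.70 it is about 1-4 points at 10-30% mortality. The gap becomes material mainly through censoring, which the follow-up rules and study end make certain for part of the cohort. All magnitudes rest on assumed mortality, effect and censoring. This should be corrected before analysis, but it does not undermine the Cox model as the adjustment tool.

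**What to change.** Keep the complete-cohort Cox model and its covariates. In the objective 3 part of section 9.7, add that:

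1. covariate-standardised mortality risks by dose group are derived from the fitted model at days 90, 180 and 270, naming the population to which they are standardised;
2. the dose effect may differ by period (to day 90, 91-180, 181-270) where the number of events permits;
3. VE is 1 minus the ratio of these risks, reported with the risk difference and with bootstrap or delta-method confidence intervals;
4. hazard ratios are secondary, labelled by their window (to day 90, 180 or 270), and not called VE.

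Bring the section 12 table description into line. The cost is a little more code in the common R script, a bootstrap run in each country if that route is chosen, and somewhat wider intervals at 9 months. No new data are needed. If the sponsor prefers hazard ratios alone, the minimum is to reword objective 3 so that it no longer promises VE at those times.
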